#### **5.1.3 Definitions**

##### **5.1.3.1 Baseline**

For clinic visit based endpoints, baseline is defined as the last record or measure collected prior to the first dose of IMP.

For IVRS based endpoints, baseline will include all available data prior to Day 1.

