### 5.4.3 Demographic Data and Baseline Characteristics

The following demographic data will be summarized by treatment group and overall for the safety, ITT and PP analysis sets:

- Age (years);
- Age group (2-5 years, 6-12 years and 13-18 years);
- Sex;
- Race;
- Country;
- Region (United States, Rest of the World);
- Weight at baseline (kg);
- Height at baseline (cm);
- Body mass index at baseline (kg/m^2).

Age will be calculated as:

$$(\text{Date of screening} - \text{date of birth}) \div 365.25.$$

The following baseline characteristics will be summarized by treatment group and overall for the safety, ITT and PP analysis sets:

- Average number of convulsive seizures per 28 days.
- Average number of non-convulsive seizures per 28 days.
- Average number of total seizures per 28 days.
- Number of patients with seizures during the baseline period, by seizure type.
- Number of antiepileptic medications a patient has used, prior to the study.
- Number of antiepileptic medications a patient is currently taking.
- Total number of prior and current antiepileptic medications.
- Number of patients taking clobazam (Yes, No, and if no, Prior).
- Number of patients taking valproic acid (Yes, No, and if no, Prior).
- Number of patients taking stiripentol (Yes, No, and if no, Prior).
- Number of patients taking levetiracetam (Yes, No, and if no, Prior).
- Number of patients taking topiramate (Yes, No, and if no, Prior).

The number of prior antiepileptic medications a patient has used will be taken from the 'History of antiepileptic medications and therapies' CRF page. The number of antiepileptic medications a patient is currently taking is based on the 'Concomitant antiepileptic medications' CRF page. If a patient has a medication listed on both the 'History of antiepileptic medications and therapies' and 'Concomitant antiepileptic medications' CRF pages, then the medication is considered concomitant (see Section 5.7.1); this will not be included in the number of prior antiepileptic medications for that patient. Antiepileptic medications starting after the last dose of IMP during the treatment period will not be counted.

Patients taking the same antiepileptic medication type, but where the medications were coded to different generic terms will be counted only once within the medication type. For example, valproate sodium, valproic acid, valproate semisodium and ergenyl chrono will all be counted as valproic acid and counted once under that term.

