The number of patients taking clobazam is defined as the number of patients taking clobazam at any point during baseline period or treatment period. The same definition will apply for the number of patients taking valproic acid, stiripentol, levetiracetam and topiramate.

Previous cannabis use will be included within the baseline characteristics listing.

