#### **5.5.5 Subgroup Analyses**

To assess the degree of effect heterogeneity, effect modifier analyses are proposed, on the ITT analysis set, for the primary efficacy endpoint and the key secondary efficacy endpoint of  $\geq 50\%$  reduction in convulsive seizure frequency.

For the primary efficacy endpoint, the effect modifier analysis will be performed using the negative binomial regression analysis as described in Section 5.5.2. The model will be updated to include covariates for each level of the effect being tested (excluding a reference level), individually and with interactions with time, interactions with treatment arm and interactions with time and treatment. A separate model will be used for testing each effect. The treatment ratios (GWP42003-P vs. placebo), percent reduction and 95% confidence intervals will be presented for each level of the effect. In addition, the effect by time by treatment arm interaction p-value, testing the hypothesis that the effect level treatment ratios are homogeneous, will be presented.

For the key secondary efficacy endpoint of  $\geq 50\%$  reduction in convulsive seizure frequency, patients with a  $\geq 50\%$  reduction in seizure frequency will be modelled using logistic regression, including stratified age group and treatment arm as covariates. The model will also include covariates for each level of the effect being tested (excluding a reference level), individually and with interactions with treatment arm. A separate model will be used for

testing each effect. The number and percent of responders, and odds ratios and 95% confidence intervals will be presented for each level of the effect. In addition, the effect by treatment arm interaction p-value, testing the hypothesis that the effect level odds ratios are homogeneous, will be presented.

The following effects will be tested:

- Age group (2-5 years, 6-12 years and 13-18 years). Note: stratified age group will be removed as a covariate for this model.
- Sex (Male, Female).
- Region (US, Rest of the World).
- Clobazam use (Yes, No).
- Valproic acid use (Yes, No).
- Stiripentol use (Yes, No).
- Clobazam use and Stiripentol use (Yes/Yes, Yes/No, No/Yes, No/No).
- Levetiracetam use (Yes, No).
- Topiramate use (Yes, No).

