- Baseline average convulsive seizure frequency per 28 days ( $\leq$  observed Tertile 1,  $>$  observed Tertile 1 to  $\leq$  observed Tertile 2,  $>$  observed Tertile 2). The observed tertile values will be rounded to the nearest whole number.
- Number of concurrent AEDs ( $<3$ ,  $\geq 3$ ).
- Number of prior AEDs ( $<4$ ,  $\geq 4$ ).
- Number of prior and concurrent AEDs ( $<8$ ,  $\geq 8$ ).

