## **5.7 Other Measures**

### **5.7.1 Concomitant Medication**

Medications will be coded using the World Health Organization Drug Dictionary, Version June 2014.

A medication will be considered concomitant if it has a start date on or after the first dose of IMP or if it was started prior to the first dose of IMP and was ongoing. If a medication has a partial or missing start/stop date and it is unclear from the date whether the medication was taken after the first dose of IMP then it will be considered concomitant.

For summaries and listings of medications the following approach will be used to determine the Anatomical Therapeutic Chemical (ATC) term to be presented:

- If coded to level 4 then the level 4 coded term will be presented.
- If coding is not performed at level 4 but level 3 coding is present then level 3 coded term will be presented.
- If coding is not performed at level 3 but level 2 coding is present then the level 2 coded term will be presented.
- If coding is not performed at level 2 but level 1 coding is present then the level 1 coded term will be presented.

Summaries of each of the following by ATC term and preferred term will be summarized by absolute counts (n) and percentages (%):

- History of antiepileptic medications;
- Concomitant antiepileptic medications;
- Concomitant rescue medications; and
- Other concomitant medications.

The ATC term, preferred term, reported generic name and reported brand name will be listed.

An additional summary table will be produced for concomitant antiepileptic therapies, displaying the number and percentage of patients with a vagus nerve stimulation device or on a ketogenic diet.

The start day and stop day will be included in the listing according to Section 5.1.2. If the date is partial and the exact day is unknown then the text 'pre' or 'post' will replace the start or stop day if it is clear from the partial date that the medication started or stopped prior to or after the first dose of IMP.

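### SAP 5.5.5 does not define its AED subgroups, and the SAP's only definition counts AEDs started after randomisation

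*SAP*

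**What the plan says.** SAP 5.4.3 lists use of clobazam, valproic acid, stiripentol, levetiracetam and topiramate among the baseline characteristics. Its definition is wider than that label: "The number of patients taking clobazam is defined as the number of patients taking clobazam at any point during baseline period or treatment period". This rule also covers the other four drugs. Under SAP 5.1.3.3 the treatment period begins on Day 1.

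The AED counts follow a similar pattern:

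- **Current AEDs.** The count comes from the concomitant AED page of the CRF. SAP 5.4.3 sets one time limit: "Antiepileptic medications starting after the last dose of IMP during the treatment period will not be counted". SAP 5.7.1 says "A medication will be considered concomitant if it has a start date on or after the first dose of IMP"; drugs begun earlier and still ongoing also qualify.
- **Prior AEDs.** The count comes from the history page. For a drug that appears on both pages, "this will not be included in the number of prior antiepileptic medications for that patient".

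SAP 5.5.5 uses five single-drug factors, a four-level clobazam-by-stiripentol factor and three AED-count factors (for example "Number of concurrent AEDs") as effect modifiers for the primary endpoint and the ≥50% responder endpoint. It gives levels and cut-points, but no time window, no data source and no reference to 5.4.3 or 5.7.1. The output includes interaction p-values; for responders this is "the effect by treatment arm interaction p-value, testing the hypothesis that the effect level odds ratios are homogeneous".

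For clinic-visit endpoints, by contrast, SAP 5.1.3.1 stops the clock before treatment: "baseline is defined as the last record or measure collected prior to the first dose of IMP".

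**The concern.** A subgroup contrast keeps the protection of randomisation only if membership is settled before treatment can influence it. Under the 5.4.3 rule, a non-user who starts clobazam on treatment moves from the No group to the Yes group. If patients start a drug because they are doing badly, the move takes poor outcomes out of one subgroup and puts them into the other. If this happens more in one arm, the two subgroup effects separate although the true effect is the same in both.

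The clobazam and clobazam-by-stiripentol interaction p-values are the SAP's check on whether the effect depends on co-medication, so a reader will rely on them for that question.

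**Working it through.** **1. Can a start after randomisation change membership?**

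- *Named drugs:* yes. Any use from Day 1 onwards makes the patient a Yes. Stopping a drug or changing its dose does not matter, because use during baseline already gives a Yes.
- *Current count:* yes. Only starts after the last treatment-period dose are left out.
- *Prior count:* only indirectly. If a drug from the history page is restarted on treatment, it leaves the prior count and joins the current count. The combined prior-and-concurrent count does not change.
- *Can such starts occur?* Protocol 8.3 prohibits new AEDs but keeps patients who take them unless there is a safety concern. SAP 4 puts AED changes on the agenda of the blinded review. No document gives a number.

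**2. Planning inputs (SAP 3.2).** Active is gamma with shape 1.0886 and scale 65.614; placebo is gamma with shape 2.3059 and scale 40.887; 62 per group. To reproduce the plan's sample size, P(active < placebo) = 0.643 by numerical integration. Noether's formula then gives a total of (1.96 + 0.84)² / [12 × 0.25 × (0.643 − 0.5)²] ≈ 127.5, or 63.8 per group. Simulated Wilcoxon power at 62 per group is 0.802. This agrees with the plan.

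**3. Simulation set-up.** 20,000 trials per setting, 62 per arm. *Assumptions:* the gammas are percent of baseline (SAP 3.2 does not say what was fitted); 31 or 40 users per arm (50% or 65%); no true interaction; no benefit from the new AED. In each affected arm, k non-users move to Yes. They are drawn at random from all non-users, at random from the worse half, or are exactly the k worst. Simulation error is about 0.15–0.3 percentage points.

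**4. Primary endpoint.** The test is a t test of the subgroup-by-arm interaction on log(percent + 1), standing in for the negative binomial mixed model. The true ratio is 0.59 in both subgroups. With no starts, rejection is 5.0–5.1%. With starts unrelated to outcome it is 4.5–5.4% for k = 1, 2 or 4. Otherwise (rejection %, 31 users / 40 users):

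| Starters | k | Placebo only | Both arms | Active only |
|---|---|---|---|---|
| Worse half | 1 | 4.8 / 5.0 | 4.8 / 4.9 | 5.0 / 5.5 |
| Worse half | 2 | 5.4 / 5.3 | 4.3 / 4.6 | 5.8 / 6.3 |
| Worse half | 4 | 6.5 / 7.0 | 4.6 / 4.8 | 9.2 / 10.5 |
| Exactly worst | 1 | 5.7 / 5.9 | 5.0 / 4.8 | 6.4 / 6.3 |
| Exactly worst | 2 | 7.0 / 7.1 | 5.0 / 5.5 | 9.3 / 10.2 |
| Exactly worst | 4 | 11.7 / 12.2 | 6.3 / 6.5 | 21.3 / 22.3 |

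The ratio of treatment ratios, No over Yes, is truly 1.00. With worse-half starts it becomes:

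| k | Placebo only | Both arms | Active only |
|---|---|---|---|
| 2 | 1.07–1.08 | 0.96 | 0.88–0.90 |
| 4 | 1.15–1.19 | 0.91–0.93 | 0.77–0.80 |

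**5. Responder endpoint.** A responder has at most 50% of baseline frequency: 49.2% on active and 26.1% on placebo. The true odds ratio is (0.492/0.508) / (0.261/0.739) = 2.74. The test is a Wald interaction test on the log odds ratio with 0.5 added per cell, standing in for the logistic model. It rejects 4.3–4.4% with no starts and 3.9–4.8% with random starts.

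- Two worse-half starts: rejection 3.7–5.4%. The No-group odds ratio becomes 2.42–2.49 (placebo only), 2.80–2.85 (both arms) or 3.06–3.23 (active only).
- Four starts: rejection 3.6–8.4% from the worse half, 5.4–11.0% if exactly the worst.

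*Hand check, placebo only, two starts:* with 31 non-users, 31 × 0.261 = 8.09 expected responders. Removing two non-responders gives 8.09/29 = 0.279, odds 0.387, and an odds ratio of 0.969/0.387 = 2.50. With 22 non-users, 5.74/20 = 0.287, odds 0.403, and the odds ratio is 2.41. Both are close to the simulated range.

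**The case against.** The link between 5.4.3 and 5.5.5 is inferred. If the 5.4.3 rule carries over, the SAP has pre-specified a wide window; if it does not, nothing shows that 5.5.5 uses on-treatment starts. Both statements are true. But no other rule exists in the SAP, and a programmer would naturally reuse the 5.4.3 variable.

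A stronger argument is rarity. Stable AEDs are an entry condition, new AEDs are prohibited, and only a new start can change a Yes/No factor. Four starts of one named drug in one arm would be 4/31 = 13% or 4/22 = 18% of its non-users. The largest figures also need those four to be exactly the worst patients, on active only, and the documents show no mechanism for that. This stands, and it is why the point is minor.

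Three limits of the simulation also stand. It covers one two-level factor, not the four-level clobazam-by-stiripentol factor or the AED counts. It uses simpler tests than the SAP. It gives the new AED no benefit. Finally, SAP 5.1.3.1 defines baseline for endpoints, not covariates, so the contrast with it is an analogy only.

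**Conclusion.** The point holds as a minor defect. The only rule the SAP offers lets an event after randomisation decide who is in an AED subgroup, and 5.5.5 does not replace it.

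The size is conditional because the number of starts is unknown. Under the assumptions above, starts unrelated to outcome, or one or two from the worse half of non-users, leave the interaction tests close to their no-start rejection rates. Material distortion needs several outcome-related starts concentrated in one arm. The direction depends on which arm that is, and the documents do not say.

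The primary and key secondary tests in SAP Table 3 are not affected. Whether seizure days after an AED change are analysed is a separate question, and nothing here depends on it.

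**What to change.** - In SAP 5.4.3, define AED use and the number of concurrent AEDs by drugs ongoing on Day 1 before the first IMP dose, and prior AEDs as those stopped before Day 1. Make 5.5.5 cite that definition.
- State how partial dates are classified, since SAP 5.7.1 makes unclear ones concomitant by default. Note that a drug stopped during baseline now counts as not used.
- Tabulate AEDs started or stopped on treatment, by arm, as a post-baseline summary.
- The any-time definition can stay as a sensitivity analysis.

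The cost is SAP wording and one extra table. No new data are needed, because SAP 5.7.1 already lists start and stop days.

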#### **5.4.4 Epilepsy and Dravet Syndrome History**

##### **5.4.4.1 Dravet Syndrome History**

The following DS history data will be summarized by treatment group and overall for the safety analysis set:

- Was development ever normal? (Yes, No, Unknown).
- If developmental delay is present, age concerns first arose (years).
- Is there intellectual disability, mental retardation or learning disability? (Yes, No).
  - If yes, how severe is the intellectual disability, mental retardation or learning disability? (Mild, Moderate, Severe, Profound, Other, Unknown).
- Was there developmental regression? (Yes, No).
  - If yes, at what age (years).
- Is the patient verbal or nonverbal? (Verbal, Non-Verbal).
  - If Verbal, extent of vocabulary (Single words, 2–3 word phrases, Long sentences, Other).
- Age patient started walking (years).
- Has any medication increased seizure frequency? (Yes, No).
- Has any medication reduced seizure frequency? (Yes, No).
- Has there been a prolonged seizure free period greater than 6 months? (Yes, No).
  - If yes, age at last occurrence (years).

##### **5.4.4.2 History of Seizures No Longer Occurring and History of Current Seizures**

Data will be summarized by treatment group and overall for the safety analysis set, separately, for history of seizures no longer occurring and history of current seizures.

The following will be summarized by each seizure type:

- Number of patients with the seizure type.
- Age at onset (years).
- Age of last occurrence (years). For history of seizures no longer occurring only.
- Seizure duration (<2 minutes, 2–10 minutes, >10 minutes, Unknown). For history of current seizures only.

Seizure frequency and trigger data will be listed only.

For patients with more than 1 record for a particular seizure type, the earliest onset, most recent age of last occurrence and longest duration will be used for the summary table.

#### **5.4.4.3 Electroencephalography History**

The following electroencephalography (EEG) history data will be summarized by treatment group and overall for the safety analysis set:

- Has the patient ever had a normal EEG? (Yes, No).
  - If yes, how old was the patient when they last had a normal EEG? (Years).
- Has the patient ever had an abnormal EEG? (Yes, No, Unknown).
- If yes:
  - EEG findings (Focal spikes, Generalized spike wave discharges, Hypsarrhythmia, Electrographic seizures).
  - Seizure type (Partial (focal) seizures, Generalized seizures, Other).
    - Generalized seizures type (Generalized spike & wave, Generalized paroxysmal fast activity, Generalized electrodecrement at onset).
  - Seizure features (Background slowing and/or disorganization, Focal slowing, Other).

#### **5.4.4.4 Neuroimaging History**

Neuroimaging history data will be listed only.

#### **5.4.5 Medical and Surgical History and Current Medical Conditions**

All conditions and diagnoses on the 'non-epilepsy medical history' CRF page will be coded using Version 17.1 of the Medical Dictionary for Regulatory Activities (MedDRA v17.1).

The number of patients with relevant or significant non-epilepsy medical or surgical history and medical history by system organ class, and preferred term, will be summarized by absolute counts (n) and percentages (%). Percentages will be calculated based on the number of patients in the specific treatment group. Two tables will be produced, one including any events classified as resolved at screening, and the other including all current conditions.

### **5.5 Efficacy Analysis**

#### **5.5.1 General Approach**

The primary analyses will use the ITT analysis set. Further analyses using the PP analysis set will also be performed for the primary endpoint and secondary endpoints where specified in the sections below.

The primary null hypothesis is:

- Following 14 weeks of treatment there is no difference in effect between the 20 mg/kg/day GWP42003-P treatment group and the placebo treatment group in terms of the change in convulsive seizure frequency during the treatment period compared to baseline.

The null hypothesis will be rejected if there is statistical evidence of a difference between the treatment groups at the  $\alpha$ -level of 0.05 for the primary endpoint.

Statistical hypothesis testing will be performed on the primary endpoint and other endpoints as appropriate. Each endpoint, including the primary will have 2 comparisons against placebo (20 mg/kg/day GWP42003-P and 10 mg/kg/day GWP42003-P vs. placebo). Also, 3 key secondary endpoints have been defined.

The primary and key secondary endpoints will be tested with their Type I error controlled by use of a hierarchical gate-keeping procedure, in the sequence given in Table 3. One must reject the null hypothesis of an endpoint at the level of 0.05 (2-sided) to test the hypothesis of the subsequent endpoint in the sequence at the level of 0.05 (2-sided). If a null hypothesis is not rejected then testing will stop and all subsequent analyses will be declared not statistically significant.

**Table 3 Hierarchy for Analysis**

Test	Endpoint	Treatment Comparison
1	Primary endpoint	20 mg/kg/day GWP42003-P vs. Placebo
2	Primary endpoint	10 mg/kg/day GWP42003-P vs. Placebo
3	1 st key secondary endpoint	20 mg/kg/day GWP42003-P vs. Placebo
4	1 st key secondary endpoint	10 mg/kg/day GWP42003-P vs. Placebo
5	2 nd key secondary endpoint	20 mg/kg/day GWP42003-P vs. Placebo
6	2 nd key secondary endpoint	10 mg/kg/day GWP42003-P vs. Placebo
7	3 rd key secondary endpoint	20 mg/kg/day GWP42003-P vs. Placebo
8	3 rd key secondary endpoint	10 mg/kg/day GWP42003-P vs. Placebo

All statistical tests will be 2-sided and use the 5% significance level.

The assumptions of normality and homogeneity of variance, for endpoints analyzed using parametric tests, will be checked where appropriate via examination of residual plots as well as computation of summary statistics for normality using the Shapiro–Wilk statistical test. If assumptions are violated then alternative non-parametric techniques will be used. In this instance the original parametric tests will be presented as a sensitivity analysis.

### 5.5.2 Primary Efficacy Endpoint

The primary endpoint is the change in convulsive seizure frequency during the treatment period (see Section 5.1.3.3) of the study compared to baseline (see Section 5.1.3.1) in patients taking GWP42003-P compared with placebo.

The primary endpoint will be analyzed using negative binomial regression on the sum of the convulsive seizure counts during the treatment period. However, convulsive seizure frequency (28-day average) and percentage change in seizure frequency will be presented using summary statistics. Percentage change from baseline in convulsive seizure frequency will be calculated as:

$$\frac{[(\text{Frequency during the treatment period} - \text{Frequency during baseline}) \div \text{Frequency during baseline}] \times 100}{}$$

The frequency during each period will be based on 28-day averages and calculated as:

$$(\text{Number of seizures in the period} \div \text{Number of reported days in IVRS in the period}) \times 28$$

For convulsive seizure endpoints only, if patients are randomized with no convulsive seizures during the baseline period then the percentage change from baseline will be calculated as:

---

(Frequency during the treatment period + 1) × 100

A mixed effect model with repeated measures will be performed modelling the observed number of convulsive seizures in the baseline period and treatment period implemented within the framework of general linear models using the negative binomial response distribution. The model will include stratified age group (2–5 years, 6–12 years and 13–18 years), time, treatment arm and treatment arm by time interaction as fixed effects and patient as a random effect. The log transformed number of days in which seizures were reported will be included as an offset. The time variable corresponds to an indicator for the baseline period and treatment period.

The GLIMMIX procedure in SAS will be utilized to perform the analysis with the option maxopt=300 applied. If the model fails to converge, then the statement 'nloptions tech=nr ridge;' will be added. If convergence is still not achieved then 'method=laplace' will be utilized. However, if convergence is still not possible, then the model will be changed to utilize the log normal response distribution (log rate model). If the log rate model is required and there are patients with a seizure frequency during the baseline or treatment period of 0 then all patients will have their baseline and treatment period seizure frequency adjusted by adding a value of 1.

The estimated ratio of least squares means for treatment period to baseline period and 95% confidence intervals (CIs) will be presented for each treatment arm. In addition, the estimated ratio of each GWP42003-P group to placebo and 95% CIs will be presented along with the p-value testing the null hypothesis that this ratio is 1.

For each ratio and upper and lower bound of the 95% CI, the percentage reduction will also be presented, calculated as:

$$[1 - (X \div Y)] \times 100\%$$

Where X corresponds to the treatment period estimate, or GWP42003-P ratio, and Y corresponds to the baseline period estimate, or placebo arm ratio.

Primary efficacy analysis will be performed using ITT analysis set.

For a period of time, the limit for the number of daily seizures for each seizure type recorded in IVRS was 99. A >99 seizure log was added to the CRF to allow the capture of the exact number of seizures where the count on a particular day was >99. When deriving the seizure frequencies, the count >99 provided on the CRF will replace the recorded 99 seizures in IVRS for the corresponding seizure type. This will only be done when the corresponding IVRS record was exactly 99.

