### **9.2.2 Visit 2 (Day 1, Randomization)**

This visit will occur 28 days after Visit 1. A visit window of +3 days from the scheduled visit date is permitted, but it is preferred that the visit is performed on the scheduled visit day where possible. Patients will be instructed to record the dosing time of their concomitant AEDs in the diary. They will also be asked to record their meal times the day before and the day of Visit 2.

The following assessments will be made at Visit 2: vital signs, postural blood pressure, physical examination (including height and body weight), details of menstruation (for females), Tanner Staging (for patients aged 10–17 [inclusive], or earlier if clinically indicated by onset of menarche or other signs of precocious puberty) and ECG. Clinical laboratory samples (blood and urine [where possible]) will be taken for hematology, biochemistry, urinalysis, a urine THC screen, determination of serum IGF-1 levels and a pregnancy test, as appropriate (using both a serum sample and urine dipstick test). The patient's IVRS report and paper diary will be reviewed and the information recorded along with information regarding AEs, epilepsy-related hospitalizations, concomitant medications and/or changes to medication (including AEDs).

The investigator must assess the patient's daily number of convulsive seizures from the patient's IVRS data. Patients who have experienced four or more convulsive seizures (i.e., tonic-clonic, tonic, clonic, atonic seizures) during the first 28 days of the baseline period, and who meet all of the other inclusion and none of the exclusion criteria specified in [Section 6](#), will be eligible to continue in the study. If a patient does not meet the eligibility criteria within this period, consideration will be given to rescreen at a later date.

Eligible patients will then be randomized to receive GWP42003-P 10 mg/kg/day, GWP42003-P 20 mg/kg/day, placebo 10 mg/kg/day dose volume equivalent, or placebo 20 mg/kg/day dose volume equivalent at a 2:2:1:1 ratio using the IVRS (see [Section 7.1](#)).

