### 5.5.2.1 Sensitivity Analyses for the Primary Efficacy Endpoint

The following sensitivity analyses will be conducted for the primary endpoint:

- Primary endpoint analysis repeated using the PP analysis set.
- Wilcoxon rank-sum test on percentage change from baseline in convulsive seizure frequency during the treatment period. An estimate of the median differences between each GWP42003-P group and placebo, together with approximate 95% CIs, will be calculated using the Hodges–Lehmann approach.
- A rank analysis of covariance (ANCOVA) on percentage change from baseline in convulsive seizure frequency during the treatment period.

The ranks of the percentage change from baseline and the baseline convulsive seizure frequency will be calculated. The rank of the percentage change from baseline will then be analyzed using an ANCOVA model with the rank of the

baseline convulsive seizure frequency and age group (2–5 years, 6–12 years and 13–18 years) as covariates and treatment group as a fixed factor. The estimated least squares means, treatment differences, together with the 95% CIs and p-values will be presented.

- ANCOVA of log transformed convulsive seizure frequency during the treatment period.

The convulsive seizure frequency during the treatment period and the baseline convulsive seizure frequency will be log transformed prior to analysis. The log transformed convulsive seizure frequency during the treatment period will then be analyzed using an ANCOVA model with the log transformed baseline convulsive seizure frequency and age group as covariates and treatment group as a fixed factor. The back transformed estimated treatment ratios, together with the 95% CIs and p-values will be presented.

If there are any patients with no seizures during the baseline or treatment periods, then 1 will be added to the convulsive seizure frequency for all patients prior to log transformation.

- ANCOVA on percentage change from baseline in convulsive seizure frequency during the treatment period including baseline and age group as covariates and treatment group as a fixed factor. The estimated least squares means, treatment differences, together with the 95% CIs and p-values will be presented.
- Primary endpoint analysis repeated using the maintenance period (see Section 5.1.3.4) rather than the treatment period.

This analysis will include only patients who have at least 7 days of seizure data within the maintenance period.

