### 5.5.3.2 Other Secondary Efficacy Endpoints

#### 5.5.3.2.1 Convulsive Seizure Treatment Responders and Convulsive Seizure Freedom

The number of patients experiencing >25% increase,  $\geq 0$  to  $\leq 25\%$  increase, >0 to <25% reduction,  $\geq 25$  to <50% reduction,  $\geq 50$  to <75% reduction or  $\geq 75\%$  reduction in convulsive seizure frequency from baseline during the treatment period will be summarized by treatment group.

In addition to the key secondary endpoint, the proportion of patients considered treatment responders, defined as those with a  $\geq 25\%$  or  $\geq 75\%$  reduction in convulsive seizure frequency from baseline and the proportion of patients who are convulsive seizure free, defined as those with a 100% reduction in convulsive seizure frequency from baseline, during the treatment period, will be summarized by treatment group and analyzed using a CMH test stratified by age as described in Section 5.5.3.1.2.

Additionally, the proportion of patients responding will be presented graphically, by treatment arm, by plotting the percent reduction against the cumulative proportion of patients achieving that level of reduction. The x-axis will be the percent reduction from baseline and the y-axis will be the proportion of patients with at least that amount of reduction, i.e.  $y = \Pr(X \geq x)$ .

Sensitivity analyses will be performed on the ITT analysis set, repeating the above analysis, using data for the maintenance period only, and during each 4 weeks of the maintenance period (Week 1–4, Week 5–8 and Week 9–12 of the 12-week maintenance period).

Analyses on the maintenance period and by each 4 weeks of the maintenance period will include only patients who have at least 7 days of seizure data within each corresponding period.

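### The SAP's percentage-change rule for patients with no baseline convulsive seizures scores a patient with no seizures in either period as a 100% increase

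*SAP*

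**What the plan says.** SAP 5.5.2 introduces the general derivation with "Percentage change from baseline in convulsive seizure frequency will be calculated as" and takes the treatment-period frequency minus the baseline frequency, divided by the baseline frequency, times 100. Both frequencies are per 28 days, using reported diary days.

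For convulsive endpoints only, a second rule follows: "if patients are randomized with no convulsive seizures during the baseline period then the percentage change from baseline will be calculated as" the quantity "Frequency during the treatment period + 1", times 100. Nothing is subtracted. No rationale is given there or in SAP 5.8, which lists changes to the planned analysis.

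The SAP deals with zeros in two other places. In the fallback log rate model (5.5.2), "all patients will have their baseline and treatment period seizure frequency adjusted by adding a value of 1". In the log-transformed ANCOVA (5.5.2.1), "then 1 will be added to the convulsive seizure frequency for all patients prior to log transformation".

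SAP 5.5.3.2.1 tabulates change categories and treats patients as convulsive seizure free if they are "defined as those with a 100% reduction in convulsive seizure frequency from baseline".

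Protocol 9.2.2 limits who can fall under the special rule: "Patients who have experienced four or more convulsive seizures" in the first 28 baseline days, and who meet the other criteria, may continue.

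**The concern.** The two rules in SAP 5.5.2 are on different scales. The general rule is a change, centred on 0. The zero-baseline rule has the form of a ratio, treatment as a percentage of baseline, centred on 100, yet its result is labelled and used as a change. The SAP does convert a ratio to a change when it reports model estimates as percentage reductions, by subtracting the ratio from 1. The zero-baseline rule has no equivalent step.

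The affected patient is the one the rule was written for. Someone with no convulsive seizures throughout would be recorded among those who worsened most. The value goes into the percentage-change summary statistics, the Wilcoxon, rank ANCOVA and percentage-change ANCOVA sensitivity analyses, the change-category table and the cumulative distribution plot.

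**Working it through.** **Inputs.** T and B are the 28-day convulsive seizure frequencies in the treatment and baseline periods (SAP 5.5.2). The longest treatment period is 99 days (SAP 5.1.3.3), so n seizures over 99 reported days give T = n ÷ 99 × 28. The category boundaries are in SAP 5.5.3.2.1.

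**Step 1: the general formula, B > 0.** Change = (T − B) ÷ B × 100.
- No change, T = B: 0.
- Doubling, T = 2B: (2B − B) ÷ B × 100 = +100.
- Seizures stop, T = 0: −100.

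**Step 2: the printed rule, B = 0.** Score = (T + 1) × 100. At T = 0 this is (0 + 1) × 100 = +100, the doubling score from step 1. Since T cannot be negative, +100 is also the minimum.

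**Step 3: the general formula with 1 added to both periods.** [(T + 1) − (0 + 1)] ÷ (0 + 1) × 100 = T × 100. The printed rule exceeds this by (T + 1) × 100 − T × 100 = 100 points at every T.

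**Step 4: numbers over 99 reported days.**

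| Seizures | T per 28 days | Printed rule | T × 100 | Category, printed | Category, T × 100 |
|---|---|---|---|---|---|
| 0 | 0 | 100.0 | 0 | >25% increase | 0 to 25% increase |
| 1 | 0.283 | 128.3 | 28.3 | >25% increase | >25% increase |
| 2 | 0.566 | 156.6 | 56.6 | >25% increase | >25% increase |
| 4 | 1.131 | 213.1 | 113.1 | >25% increase | >25% increase |
| 14 | 3.960 | 496.0 | 396.0 | >25% increase | >25% increase |

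Only T = 0 changes category. One seizure in 99 days already gives 28.3%, and fewer reported days would give more.

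**Step 5: where the value does and does not reach.**
- Primary test: a negative binomial model on counts. It does not use percentage change.
- Responders at 25, 50 and 75% reduction: both formulas give values of 0 or more, so the patient is a non-responder either way.
- Percentage-change ANCOVA: one affected patient in a group of 62 raises that group's raw mean by 100 ÷ 62 = 1.6 points.
- Wilcoxon and rank ANCOVA: ranks move only if other patients' values lie between T × 100 and (T + 1) × 100.
- Seizure freedom: this requires a score of −100. At T = 0 the printed rule gives +100 and T × 100 gives 0. Neither qualifies.

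**The case against.** Percentage change from a zero baseline is undefined, so any value is a convention, and the SAP does not say that 1 is added to both periods for this rule. The add-one steps it does describe are for log-scale models and apply to all patients once any patient has a zero; here only zero-baseline patients would be adjusted. A deliberately unfavourable score for them would also fit the text. This stands to the extent that T × 100 is the most natural repair, not a value the SAP establishes. It does not rescue the printed rule: the +100% for a patient with no seizures at all follows from the formula as written, and no penalty is stated.

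A reader might also infer more than the documents support:
- That responder rates or the primary result are distorted. Neither can be, as the working shows.
- That the missing subtraction is why these patients cannot be seizure free. The cause is the 100%-reduction definition, and subtracting 1 does not cure it.
- That a specific patient is affected. SAP 5.2.2 mentions one patient randomized in error, but says nothing of that patient's baseline count. The patient received no study medication and is excluded from the ITT set. The documents give no number of zero-baseline patients.

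**Conclusion.** The point holds as a minor error of derivation. It is exact, with no assumption beyond the printed text, that a patient with no convulsive seizures in either period scores +100% and is tabulated among the increases above 25%. That the rule is 100 points too high at every T rests on reading it as add-one in both periods, which is inferred from SAP 5.5.2 and 5.5.2.1.

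The practical effect is confined to ITT patients with no baseline convulsive seizures. The entry criterion implies few or none, since such a patient would have been randomized against it. The seizure-freedom gap is a separate problem affecting the same patients.

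**What to change.** In SAP 5.5.2, replace the zero-baseline expression with [(T + 1) − 1] × 100 = T × 100. If the offset is intended, state that and give the reason.

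In SAP 5.5.3.2.1, add one sentence: patients with no baseline convulsive seizures are classified as seizure free or not from whether their treatment-period count is zero.

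The cost is one formula and one sentence, with the matching lines in the derivation program. No data collection, sample size or primary analysis changes. Both edits should be made before unblinding, and reporting the number of zero-baseline patients in the ITT set would show whether the rule was ever used.
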